## **8.0 REGULATORY AND REPORTING REQUIREMENTS**

The Principal Investigator is responsible for ensuring the safety of subjects who have enrolled in the study. The PI will monitor the study for adverse events directly attributable to participation in this study (i.e. events associated with the research specimen collections and QOLs, not events associated with routine administration of temozolomide). Because the care obtained while on trial is indicated and standard of care, no adverse events are likely to be attributable to enrollment. If any breach of confidentiality were to occur, it would be reported according to the HRPO-recommended guidelines.

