### **1.7 Study Rationale**

Temozolomide (TMZ) is the chemotherapy drug approved by the FDA to increase survival in glioblastoma (GBM) patients beyond surgical resection and radiation therapy alone. Give its activity in astrocytomas, TMZ is commonly used in grade III anaplastic astrocytoma (AA) as well. Both grade III AA and grade IV GBM are high grade gliomas

(HGG). The short half-life of this drug and known oscillations in DNA damage repair make it an ideal candidate for chronotherapy. Chronotherapy has improved outcomes through the reduction of side effects and increase in anti-tumor activity for a variety of cancers, but has never been applied to the treatment of gliomas. Based on the preliminary preclinical data for chronotherapeutic TMZ treatment of intracranial glioma xenografts and the success of chronotherapy in the treatment of other cancers, we hypothesize that the timing of TMZ treatment will alter its efficacy and toxicity.

These effects will be assessed by the following means:

1. Randomized assignment of patients to one of two treatment time frames (before 10:00 versus after 20:00).
2. Measurement of hematologic toxicity throughout treatment.
3. Assessment of QOL through surveys.
4. Correlation of PFS and OS to chronotherapeutic treatment windows.
5. Assessment of daily rest-activity rhythms as well as overall daily activity.

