#### **4.4 Randomization**

Eligible patients will be randomized on a 1:1 basis to receive temozolomide at one of two time points: before 10:00 or after 20:00. A computer-generated randomization scheme is used to assign subjects. It is maintained centrally by the study statistician.

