## **12.0 DATA AND SAFETY MONITORING**

In compliance with the Washington University Institutional Data and Safety Monitoring Plan, the Principal Investigator will provide a Data and Safety Monitoring (DSM) report to the Washington University Quality Assurance and Safety Monitoring Committee (QASMC) semi-annually beginning six months after accrual has opened (if at least five patients have been enrolled) or one year after accrual has opened (if fewer than five patients have been enrolled at the six-month mark).

The Principal Investigator will review all patient data at least every six months, and provide a semi-annual report to the QASMC. This report will include:

- HRPO protocol number, protocol title, Principal Investigator name, data coordinator name, regulatory coordinator name, and statistician
- Date of initial HRPO approval, date of most recent consent HRPO approval/revision, date of HRPO expiration, date of most recent QASMC audit, study status, and phase of study
- History of study including summary of substantive amendments; summary of accrual suspensions including start/stop dates and reason; and summary of protocol exceptions, error, or breach of confidentiality including start/stop dates and reason
- Study-wide target accrual and study-wide actual accrual
- Protocol activation date
- Average rate of accrual observed in year 1, year 2, and subsequent years
- Expected accrual end date and accrual by cohort
- Objectives of protocol with supporting data and list the number of participants who have met each objective
- Measures of efficacy
- Early stopping rules with supporting data and list the number of participants who have met the early stopping rules
- Summary of toxicities separated by cohorts
- Abstract submissions/publications
- Summary of any recent literature that may affect the safety or ethics of the study

The study principal investigator and Research Patient Coordinator will monitor for serious toxicities on an ongoing basis. Once the principal investigator or Research Patient Coordinator

becomes aware of an adverse event, the AE will be reported to the HRPO and QASMC according to institutional guidelines.

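### Section 8.0 takes temozolomide toxicity out of the PI's adverse-event monitoring, although dosing time is what the trial randomises and Sections 12.0 and 13.2.2.1 cover the same events

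*Combined protocol and SAP*

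**What the plan says.** Section 8.0 has the PI monitor adverse events directly attributable to taking part, and spells these out as "events associated with the research specimen collections and QOLs, not events associated with routine administration of temozolomide". Its reason follows: "Because the care obtained while on trial is indicated and standard of care, no adverse events are likely to be attributable to enrollment".

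Section 4.4 describes the intervention: "Eligible patients will be randomized on a 1:1 basis to receive temozolomide at one of two time points: before 10:00 or after 20:00". Section 1.7 gives the hypothesis: "we hypothesize that the timing of TMZ treatment will alter its efficacy and toxicity". The first secondary objective in 2.2 is the number of patients with grade 3 or 4 haematologic toxicity under morning or evening dosing.

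Section 12.0 says that the PI and the patient coordinator "will monitor for serious toxicities on an ongoing basis". An AE that comes to their notice goes to the HRPO and the QASMC under institutional guidelines. The semi-annual report to the QASMC must contain, among other items, supporting data for each protocol objective, "Summary of toxicities separated by cohorts" and "Early stopping rules with supporting data and list the number of participants who have met the early stopping rules".

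Section 13.2.2.1 puts every AE in a listing, classes each as related or unrelated to study drug, and plans separate summaries of drug-related AEs, AEs of grade 3 or worse, AEs leading to interruption, modification or discontinuation, and SAEs.

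**The concern.** The reasoning in 8.0 would suit an observational study added to routine treatment. In this trial, enrolment itself decides when the drug is taken, and the protocol expects that to matter for toxicity. If one dosing time is more toxic, the excess is attributable to participation, yet 8.0 places it with background events of standard care. A site that follows 8.0 literally would not monitor the one kind of harm that the randomised intervention could cause. A site that follows 12.0 would. Safety oversight then depends on which section is read.

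**Working it through.** No arithmetic applies: the point rests on no rate, sample size or error probability. The check sets the sections side by side.

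1. **What 8.0 keeps.** Its list names research specimen collections and questionnaires. The study calendar (9.0) contains no research specimen collection, and its second footnote takes haematology from standard-of-care draws. The actimetry watch, which is a research procedure, is not named. In practice the list covers little beyond the questionnaires, plus breaches of confidentiality, which 8.0 handles separately.

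2. **What 8.0 removes.** It removes events of routine temozolomide administration. The list does not mention dosing time, and the sentence after it treats all on-trial care as standard. An excess of toxicity at one dosing time has no place in the retained class.

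3. **What the other sections do with the same events.**

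| Section | Temozolomide toxicity |
|---|---|
| 8.0 | Outside PI monitoring |
| 12.0 | Serious toxicities monitored continuously; AEs reported under institutional guidelines; toxicities summarised semi-annually |
| 13.2.2.1 | All listed, related to study drug, summarised by grade and seriousness |

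No section says which takes precedence.

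4. **Haematologic events.** These are an objective (2.2), have grading thresholds (5.2.1), a calendar row at each cycle (9.0), a monthly form (10.0) and a secondary endpoint (13.1.2). They are captured however 8.0 is read. The objectives item in the 12.0 report should also bring them to the QASMC by arm, because the objective is worded by dosing time. What remains is a conflict over the scope of monitoring and reporting.

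5. **Non-haematologic events.** The calendar has no AE row, and the CRF schedule lists no AE or SAE form. Section 13.2.2.1 nevertheless promises full TEAE and SAE tables. The objectives name no non-haematologic toxicity, so the objectives item does not bring these events into the report. They depend on the general toxicity monitoring in 12.0, which 8.0 contradicts.

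6. **Whether attribution case by case can resolve it.** In one patient, a toxicity due to the assigned hour looks the same as ordinary temozolomide toxicity. A timing effect shows only when the arms are compared. The toxicity item in 12.0 is split by cohort, a term used there and in 13.2.1 but never defined or equated with the arms. Eligibility (3.1) offers other possible groupings: newly diagnosed or recurrent disease, and WHO grade.

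**The case against.** The best defence is that the two sections do different jobs: 8.0 covers events from research procedures, 12.0 covers drug toxicity, and 8.0 opens by making the PI responsible for subject safety in general. The word for routine administration might also exclude only harm unrelated to the assigned time. Either reading is possible, but the text states neither, and step 6 shows why the second could not be applied patient by patient.

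Several counter-arguments stand and limit the point:

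- A reader might infer that an imbalance between arms could stay hidden from the committee until the final analysis. The documents do not support that. The objectives item calls for supporting data on haematologic toxicity by dosing time, and under 12.0 the PI goes through all patients' data at least six-monthly.
- A reader might take the interval between semi-annual reports, counted in treatment cycles, as the delay in detection. That assumes events reach the QASMC only through the report, whereas 12.0 also provides for reporting when the PI or coordinator learns of an AE. Such a count would measure calendar time, not patient exposure.
- A reader might conclude that 12.0 requires individual reporting of every temozolomide event and that following 8.0 must cause under-reporting. Reporting under 12.0 is qualified by institutional guidelines that are not in the documents, so this cannot be established.
- The randomised arms are the natural reading of cohort, since they are the only division of patients that the protocol creates. That item is a matter of terminology, and pooling over arms is not shown.

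**Conclusion.** The concern holds as an inconsistency in the stated rules. Read literally, 8.0 excludes from PI monitoring the class of harm that the randomised intervention could cause, for a reason that contradicts the study hypothesis, and it conflicts with 12.0 and 13.2.2.1. For haematologic toxicity the consequence is confined to monitoring and reporting scope; data capture is intact. The practical gap is larger for other temozolomide toxicities, because the planned tables have no listed source of data. The documents give no basis for a numerical size.

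Two assumptions matter: that the calendar and CRF schedule are complete as listed, and that the institutional guidelines, which could not be seen, do not themselves settle what the PI monitors. The change should be made because it is cheap and concerns safety oversight. It does not imply that any toxicity has been or will be missed.

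**What to change.** - **Section 8.0:** delete the exclusion of temozolomide events and the statement that "no adverse events are likely to be attributable to enrollment". State that toxicities after randomisation are monitored, reported and analysed under 12.0 and 13.2.2.1.
- **Section 12.0:** have the toxicity summary separated by randomised arm (before 10:00 / after 20:00), with the number of patients and the number of cycles started in each arm as denominators.
- **Sections 9.0, 10.0 and 13.2.2.1:** reconcile them. Either add an AE assessment and form that can support the TEAE and SAE tables, or reduce those tables to what is collected.
- **Separate minor point:** the report in 12.0 asks for counts against early stopping rules, but the protocol states none. Reconcile the item with the protocol.

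The changes to 8.0 and 12.0 are wording for the next amendment, and the by-arm table uses assignments already held and haematologic data already collected. The real cost lies in non-haematologic events: some extra recording by the coordinator and possibly a new AE form.

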## 9.0 STUDY CALENDAR

	Baseline	Beginning of each cycle of TMZ	1 month after the last TMZ treatment 	Follow-up 
Informed consent	X			
ActTrust Condor Instrument watch		Continuously beginning after the signing of consent but no more than 2 weeks prior to initiation of TMZ		
Sleep Questionnaire	X	X	X	
FACT-Br	X	X	X	
Randomization	X			
Tracking of hematologic toxicity 		X		
Review of medical record				X

1. Every 3 months by chart review looking for progression and survival.

2. From SOC blood draws.

3. To coincide with the patient's SOC end of treatment follow up visit with treating physician.

## 10.0 DATA SUBMISSION SCHEDULE

Case report forms with appropriate source documentation will be completed according to the schedule listed in this section.

Case Report Form	Submission Schedule
Original Consent Form	Prior to registration
Registration Form Eligibility Form On-Study Form FACT-Br Randomization Form Quality of Sleep Questionnaire	Prior to starting treatment
Hematologic Toxicity Form	Monthly
Medication Diary	End of every cycle
FACT-Br Quality of Sleep Questionnaire	Beginning of each cycle 1 month after EOT
Follow-Up Form	Every 3 months until 24 months after active participation

## 11.0 MEASUREMENT OF EFFECT

### 11.1 Antitumor Effect – Solid Tumors

For the purposes of this study, patients should be re-evaluated for response every 8 +/- 1 weeks. After the first year, scans may go to every 12 weeks +/- 1 week. After the second year,

scans may go to every 16 weeks +/- 1 week, depending on physician choice. In addition to a baseline scan, confirmatory scans should also be obtained 8 weeks (not less than 4) weeks following initial documentation of objective response.

Response and progression will be evaluated in this study using the updated response assessment criteria for high-grade gliomas: Response Assessment in Neuro-Oncology (RANO) working group guideline [JCO 28(11): 1963-1972, 2010].

Criteria for Determining First Progression Depending on Time from Initial Chemoradiotherapy

First Progression	Definition
Progressive disease < 12 weeks after completion of chemoradiotherapy	Progression can only be defined using diagnostic imaging if there is new enhancement outside of the radiation field (beyond the high-dose region or 80% isodose line) or if there is unequivocal evidence of viable tumor on histopathologic sampling (eg, solid tumor areas [ie, > 70% tumor cell nuclei in areas], high or progressive increase in MIB-1 proliferation index compared with prior biopsy, or evidence for histologic progression or increased anaplasia in tumor). Note: Given the difficulty of differentiating true progression from pseudoprogression, clinical decline alone, in the absence of radiographic or histologic confirmation of progression, will not be sufficient for definition of progressive disease in the first 12 weeks after completion of concurrent chemoradiotherapy.
Progressive disease $\geq$ 12 weeks after chemoradiotherapy completion	
 
1. New contrast-enhancing lesion outside of radiation field on decreasing, stable, or increasing doses of corticosteroids.
 
2. Increase by <math>\geq 25\%</math> in the sum of the products of perpendicular diameters between the first postradiotherapy scan, or a subsequent scan with smaller tumor size, and the scan at 12 weeks or later on stable or increasing doses of corticosteroids.
 
3. Clinical deterioration not attributable to concurrent medication or comorbid conditions is sufficient to declare progression on current treatment but not for entry onto a clinical trial for recurrence.
 
4. For patients receiving antiangiogenic therapy, significant increase in T2/FLAIR nonenhancing lesion may also be considered progressive disease. The increased T2/FLAIR must have occurred with the patient on stable or increasing doses of corticosteroids compared with baseline scan or best response after initiation of therapy and not be a result of comorbid events (eg, effects of radiation therapy, demyelination, ischemic injury, infection, seizures, postoperative changes, or other treatment effects).
 

Criteria for Response Assessment Incorporating MRI and Clinical Factors (Adapted from JCO 2010)

Response	Criteria
Complete response	
 
• Requires all of the following: complete disappearance of all enhancing measurable and nonmeasurable disease sustained for at least 4 weeks.
 
• No new lesions; stable or improved nonenhancing (T2/FLAIR) lesions.
 

Response	Criteria
	
 
Patients must be off corticosteroids (or on physiologic replacement doses only) and stable or improved clinically. Note: Patients with nonmeasurable disease only cannot have a complete response; the best response possible is stable disease.
 

Partial response	
Requires all of the following:
 
 
≥ 50% decrease compared with baseline in the sum of products of perpendicular diameters of all measurable enhancing lesions sustained for at least 4 weeks.
 
No progression of nonmeasurable disease.
 
Stable or improved nonenhancing (T2/FLAIR) lesions on same or lower dose of corticosteroids compared with baseline scan; the corticosteroid dose at the time of the scan evaluation should be no greater than the dose at time of baseline scan.
 
Stable or improved clinically. Note: Patients with nonmeasurable disease only cannot have a partial response; the best response possible is stable disease.
 

Stable disease	
Requires all of the following:
 
 
Does not qualify for complete response, partial response, or progression.
 
Stable nonenhancing (T2/FLAIR) lesions on same or lower dose of corticosteroids compared with baseline scan. In the event that the corticosteroid dose was increased for new symptoms and signs without confirmation of disease progression on neuroimaging, and subsequent follow-up imaging shows that this increase in corticosteroids was required because of disease progression, the last scan considered to show stable disease will be the scan obtained when the corticosteroid dose was equivalent to the baseline dose.
 

Progression	
Defined by any of the following:
 
 
≥ 25% increase in sum of the products of perpendicular diameters of enhancing lesions compared with the smallest tumor measurement obtained either at baseline (if no decrease) or best response, on stable or increasing doses of corticosteroids*. The absolute increase in any dimension must be at least 5mm when calculating the products.
 
Significant increase in T2/FLAIR nonenhancing lesion on stable or increasing doses of corticosteroids compared with baseline scan or best response after initiation of therapy not caused by comorbid events (e.g. radiation therapy, demyelination, ischemic injury, infection, seizures, postoperative changes, or other treatment effects).
 
Any new measureable lesion.
 
Clear clinical deterioration not attributable to other causes apart from the tumor (e.g. seizures, medication adverse effects, complications of therapy, cerebrovascular events, infection, and so on) or changes in corticosteroid dose.
 

Response	Criteria
	
 
Failure to return for evaluation as a result of death or deteriorating condition; or clear progression of nonmeasurable disease.
 

- NOTE. All measurable and nonmeasurable lesions must be assessed using the same techniques as at baseline.
- Stable doses of corticosteroids include patients not on corticosteroids.

## 11.2 Disease Parameters

**Measurable disease:** Bi-dimensionally measurable lesions with clearly defined margins by MRI scan. All tumor measurements must be recorded in millimeters (or decimal fractions of centimeters).

**Non-measurable or evaluable disease:** Uni-dimensionally measurable lesions or lesions with margins not clearly defined such as areas of T2/FLAIR signal abnormality or poorly defined enhancing abnormality.

Note: For cystic lesions, the only measurable part is any enhancement area around the cyst that is clearly defined and bi-dimensionally measurable. The cyst itself should not be considered measurable or non-measurable disease.

**Target lesions:** All measurable lesions that are residual of the lesion treated with MLA should be identified as target lesions and recorded and measured. Target lesions should be selected on the basis of their size (lesions with the longest diameter), but in addition should be those that lend themselves to reproducible repeated measurements. It may be the case that, on occasion, the largest lesion does not lend itself to reproducible measurement in which circumstance the next largest lesion, which can be measured reproducibly should be selected. When there are too many measurable lesions, choose the largest three lesions as target lesions to follow. The other measurable lesions should be considered evaluable for the purpose of objective status determination.

**Non-target lesions:** All non-measurable lesions should be identified as non-target lesions and should also be recorded at baseline. Measurements of these lesions are not required, but the presence, absence, or in rare cases unequivocal progression of each should be noted throughout follow-up.

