# A Randomized Feasibility Study Evaluating Temozolomide Chronotherapy for High Grade Glioma

## SCHEMA

## Glossary of Abbreviations

AE	Adverse event
CBV	Cerebral Blood Volume
CNS	Central nervous system
CR	Complete response
CRF	Case report form
CT	Computed tomography
CTCAE	Common Terminology Criteria for Adverse Events
DNA	Deoxyribonucleic acid
DOB	Date of Birth
DSM	Data and Safety Monitoring
HRPO	Human Research Protection Office (IRB)
HGG	High Grade Glioma
IRB	Institutional Review Board
MD	Medical Doctor
MLA	Minimal lumen area
MRI	Magnetic resonance imaging
NCI	National Cancer Institute
ORR	Overall response rate
OS	Overall survival
PD	Progressive disease
PFS	Progression Free Survival
PI	Principal investigator
PR	Partial response
QASMC	Quality Assurance and Safety Monitoring Committee
QOL	Quality of Life
RANO	Response Assessment in Neuro-Oncology
SAE	Serious adverse event
SAP	Statistical analysis plan
SD	Stable disease
T2/FLAIR	T2-weighted Fluid Attenuated Inversion Recovery
TEAE	Treatment-emergent adverse events
TMZ	Temozolomide
UPN	Unique patient number
WHO	World Health Organization

[figure not shown]

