## **3.0 PATIENT SELECTION**

### **3.1 Inclusion Criteria**

1. **Newly diagnosed and recurrent high grade gliomas (WHO grades III & IV) and high risk WHO grade II gliomas who are to begin treatment with monthly high dose temozolomide therapy.**
2. At least 18 years of age.
3. Karnofsky performance status  $\geq 60\%$ , see Appendix A
4. Ability to understand and willingness to sign an IRB approved written informed consent document.

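### Section 11 has three errors in its response and progression rules: target lesions tied to MLA, conflicting FDG-PET sentences, and a target-lesion progression rule that does not match the table in 11.1

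*Combined protocol and SAP*

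**What the plan says.** All places are in the combined protocol and SAP.

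- **Overall standard.** Section 11.1: "Response and progression will be evaluated in this study using the updated response assessment criteria for high-grade gliomas", that is, RANO. Section 13.2.1 also names RANO for duration of response.
- **Target lesions.** Section 11.2: "All measurable lesions that are residual of the lesion treated with MLA should be identified as target lesions and recorded and measured". The glossary entry for MLA is "Minimal lumen area". The same section then gives selection rules (size, reproducibility, the three largest if there are many) and defines non-target lesions as the non-measurable ones.
- **FDG-PET.** In 11.3 the first sentence of the entry allows it as an adjunct test. The second says it should serve as the primary or only method. The Perfusion/CBV entry just above has the same two-sentence structure, but its second sentence is negated.
- **Progression by size, response table in 11.1.** At least a 25% "increase in sum of the products of perpendicular diameters of enhancing lesions compared with the smallest tumor measurement" at baseline or best response, with the corticosteroid dose steady or rising and growth of at least 5 mm in a dimension.
- **Progression by size, 11.3.1.** At least a 25% increase in at least one target lesion against the smallest sum on study, with the 5 mm minimum. Corticosteroids are not mentioned.
- **Progression in non-target lesions, 11.3.2.** The corticosteroid condition is present.
- **Use of the dates.** PFS (11.3.6) runs from start of treatment to progression or death and refers to none of these rules. Follow-up in the study calendar is "Every 3 months by chart review looking for progression and survival".

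**The concern.** These are operative outcome rules. An assessor who follows 11.3.1 or the FDG-PET entry as written can date progression differently from one who follows the response table in 11.1. The date enters PFS (secondary endpoint 3) and duration of response, both of which 13.2.1 analyses by Kaplan-Meier. Section 2.0 says the study is meant to supply pilot data for later chronotherapy studies, so progression dates should be reproducible even though they are only described here. PFS may also be taken from charts, and 11.3.6 does not tell the abstractor which of the rules in Section 11 fixes the date.

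**Working it through.** The plan gives no figure to reproduce. The check sets the rules side by side and applies two of them to assumed lesions.

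**(a) MLA.** The study plan (4.4 and 5.1) contains one intervention, the time of day at which standard temozolomide is taken. No procedure called MLA appears, and the glossary meaning is a measurement, not a treatment. Taken literally, the set of lesions treated with MLA is empty. Because 11.2 reserves the non-target class for non-measurable lesions, a measurable lesion would then be neither target nor non-target, and 11.3.1 would have nothing to act on. Without the MLA clause, the rest of the paragraph is a complete selection rule.

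**(b) FDG-PET.** An adjunct test cannot also be the primary or only method. The perfusion entry has the same construction with a negation, so a dropped word is the likely cause.

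**(c) Size rule for progression.**

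| Rule | Quantity | Threshold | 5 mm minimum | Corticosteroid dose steady or rising |
|---|---|---|---|---|
| 11.1 response table | sum over enhancing lesions | 25% | yes | required |
| 11.3.1 target lesions | at least one target lesion | 25% | yes | not stated |
| 11.3.2 non-target lesions | unequivocal progression | none | none | required |

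The sizes below are assumptions chosen to illustrate. No other progression criterion (new lesion, T2/FLAIR, clinical decline) is taken to be met.

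*Illustration 1, corticosteroid condition.* One target lesion grows from 20x20 to 25x25 mm while the dose is being reduced.
- Change = (25 × 25)/(20 × 20) − 1 = 625/400 − 1 = +56.25%, with 5 mm growth per side.
- 11.3.1: progression. 11.1 size rule: not met, because the dose is falling.

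*Illustration 2, one lesion or the sum.* Two target lesions of 30x30 and 10x10 mm, dose stable; the smaller grows to 15x15 mm.
- Smaller lesion: 225/100 − 1 = +125%, with 5 mm growth per side.
- Sum: (900 + 225)/(900 + 100) − 1 = 1125/1000 − 1 = +12.5%.
- 11.3.1 read as a single-lesion rule: progression. 11.1 size rule: not met, because 12.5% is below 25%.

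*Possible shift in date.* The documents do not allow an estimate. As a scenario only, a call deferred by one scheduled scan would move by 7 to 9 weeks in the first year (8 ± 1 weeks in 11.1), and by 11 to 13 or 15 to 17 weeks later if the 12-week or 16-week schedule is used.

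**The case against.** The best defence is that RANO governs through the opening of 11.1, that the two text slips are obvious to any reader, and that 11.3.1 is only a component rule. Section 11.3.5 adds neurological function and performance status to the overall assessment, which fits that reading. Some of this stands: (a) and (b) are editorial in origin, and most assessors would read past them. But every conflicting rule sits under the RANO statement as its implementation, no order of precedence is given, and 11.3.2 repeats the corticosteroid condition that 11.3.1 leaves out. The sum in 11.3.1 could also be read as running over all target lesions. Its mention of at least one lesion leaves that open, so Illustration 2 depends on the reading.

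Several stronger inferences are tempting but not supported.

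- *That response cannot be assessed at all.* The selection rule in 11.2 works without the MLA clause, and the progression list in 11.1 does not depend on it.
- *That the summary table in 11.3.3 sides with 11.3.1,* because it marks corticosteroids as not applicable to progression. It is labelled a summary. Its note says only that a corticosteroid increase alone does not establish progression without persistent clinical deterioration. It does not say that growth on a falling dose is progression.
- *That the two tables in 11.1 contradict each other.* One measures growth "between the first postradiotherapy scan, or a subsequent scan with smaller tumor size, and the scan at 12 weeks or later" and has no 5 mm minimum; the other uses baseline or best response and has one. But the former is headed "Criteria for Determining First Progression Depending on Time from Initial Chemoradiotherapy", so the stated scopes differ. What remains is that the protocol does not say when each applies, although it enrols "Newly diagnosed and recurrent high grade gliomas (WHO grades III & IV) and high risk WHO grade II gliomas".
- *That a chart abstractor has no standard.* RANO is named. What is missing is a ranking of the rules beneath it.
- *That secondary endpoint 5 is affected.* The correlation variables in 13.2.1 include tumor size, but not response category or progression date, so no effect is shown.

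**Conclusion.** The point holds: the three rules are wrong as written, and the matter is minor. The MLA clause and the FDG-PET conflict are plain from the text. The mismatch between 11.3.1 and the response table is also textual, and its corticosteroid part rests on no assumption about which patients fall under the first-progression table. The illustrations show that one scan can be classified in two ways; they do not show how often. Neither the number of patients affected nor any actual shift in PFS can be derived from the documents. The primary compliance endpoint, the sample size of 40 and overall survival do not depend on these rules.

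**What to change.** One protocol amendment with four wording changes:

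1. **11.2:** delete the clause that ties target lesions to a lesion treated with MLA, and keep the rest of the paragraph.
2. **11.3, FDG-PET entry:** insert the word not in the second sentence, so that it matches the perfusion entry.
3. **11.3.1:** reconcile the progression rule with the RANO response table in 11.1, using the sum of products and the same corticosteroid and 5 mm conditions.
4. **11.3.6:** name the table in 11.1 that governs progression dates for PFS and duration of response, including dates taken by chart review. State when the first-progression table applies; that scope is for the sponsor to set.

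No new procedures or visits are needed. The cost is that progression dates already recorded may have to be re-checked, and some may change. The re-check should preferably be done without knowledge of the assigned arm.
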